#### 3.2.2 Assessment of grip strength of the affected side

The AOPI Opi EH101 electronic grip device was used to detect the grip strength of the affected side. The test method was as follows: the patient stood up straight, the arm was drooped, and the affected hand grasped the grip meter to grasp the grip strength. A total of 2 measurements were performed, and the average value of the two tests was taken and recorded in kg.

#### 3.2.3 Shoulder range of motion measurement

ROM of the upper limb of breast cancer patients was measured with a circular protractor (0° -360°) manufactured by Handan Jiuxu Medical Device Co., LTD. The range of motion of the upper extremity was measured by the rehabilitation technologist in 6 directions: forward flexion, posterior extension, abduction, adduction, internal rotation and external rotation.

#### 3.2.4 Subjective assessment of upper limb dysfunction

The Chinese version of DASH scale, adapted from the DASH scale developed by Beaton, was used to evaluate the upper limb condition of the patients. Cronbach's A coefficient was 0. 911 and intra-group correlation coefficient was 0. 882. The highest score is 100 and the lowest is 0, with higher scores indicating more severe upper arm problems.

#### 3.2.5 Quality of life evaluation of breast cancer patients

The FACT-B 4.0 scale developed by Cella and translated by Wan Chonghua was used to measure the quality of life of patients. The correlation R value between each dimension and the total scale was more than 0.65, and the Cronbach's  $\alpha$  of each dimension was 0.61-0.84, which is one of the most commonly used scales to evaluate the quality of life of breast cancer patients. It contains 5 dimensions, a total of 36 items, using a 5-level score, the higher the score, the higher the quality of life of patients.

#### 4 Data analysis

SPSS21.0 software was used, a two-sided test was set, and  $\alpha$  was set at 0.05. The normality of measurement data was expressed as mean  $\pm$  standard deviation ( $\pm s$ ), and two independent sample t-test was used. When not normal, the median and interquartile range [M(Q)] were expressed using the Mann-Whitney U test. Enumeration data were expressed as frequency and constituent ratio using 2 test. Mann-whitney U test was used for grade data.

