## 2.3 Power analysis

This study used PASS 15.0 to calculate the sample size, using two-sided test,  $\alpha = 0.05$  and  $1 - \beta = 0.8$ . According to the literature,  $P_1$  was taken as 30% and  $P_2 = 5\%$ . The final calculation yielded  $N_1 = N_2 = 44$ , considering the 20% loss to follow-up rate after surgery, and the final total sample size was set at 106 cases, with 53 cases in the intervention group and 53 cases in the control group.

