### 3.1 Data collection

The data collection personnel were trained uniformly, and the collection personnel were not aware of the grouping of patients. Before the intervention, the whole process of the prevention program, its purpose and significance were explained to the patients in detail, and the patients were asked to fill in the informed consent form, telling the patients that they had the right to withdraw from the trial at any time.

Considering the compliance of patients in the survey, this study collected data from patients at three time periods. The baseline data of patients before intervention were collected in stage 1 (T0), stage 2 (T1) was the third time for chemotherapy (21 days as a chemotherapy cycle), and stage 3 (T2) was the sixth time for chemotherapy.

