#### 5 RESULTS

In this study, a total of 108 patients completed the baseline survey (T0), 56 in the control group and 52 in the intervention group. A total of 11 patients fell off during the study (6 in the control group and 5 in the intervention group), and a total of 97 patients completed the study (50 in the control group and 47 in the intervention group), as shown in Figure 1.

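### Section 4 names only two-sample tests for outcomes measured three times; a likelihood-based mixed model would use the baseline and any T1 data for the continuous outcomes, and lymphedema needs a tipping-point table

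*Protocol*

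**What the plan says.** Section 3.1 states that "this study collected data from patients at three time periods": T0 before the intervention, T1 at the third chemotherapy and T2 at the sixth.

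Section 4 fixes the analysis by type of data:

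- normally distributed measures: "two independent sample t-test was used";
- non-normal measures: medians that "were expressed using the Mann-Whitney U test";
- counts: "Enumeration data were expressed as frequency and constituent ratio using 2 test", which I read as chi-square with its symbol lost in text extraction;
- ordered categories: "Mann-whitney U test was used for grade data".

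The section mentions no visits, no baseline adjustment and no repeated-measures model. Section 5 reports 108 patients at baseline (56 control, 52 intervention). It then says "A total of 11 patients fell off during the study", 6 control and 5 intervention, leaving 97 completers (50 and 47).

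**The concern.** Section 4 makes a positive choice of method, so this is more than a detail left to an analysis plan. A two-sample test at T2 uses only patients with a T2 value and looks only at that value. Two kinds of collected information go unused:

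- the T0 value of every patient, which for grip strength, range of motion, DASH, FACT-B and limb volume should predict the T2 value;
- any T1 value of patients who left between T1 and T2.

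A completers-only comparison is also unbiased only if, within each arm, those who stayed are representative of those who started. A likelihood-based model needs less: loss may depend on values already observed. At stake are the precision of the continuous outcomes and, for lymphedema, whether 11 unknown outcomes could change the conclusion when few intervention-arm cases are expected.

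**Working it through.** **Inputs from the protocol.** Rates 30% and 5%, two-sided alpha 0.05, power 0.80, 44 evaluable per arm (section 2.3); 56 and 52 at T0, 6 and 5 lost, 50 and 47 completers (section 5); literature incidence 21.4% (section 1).

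**Assumed, not in the protocol.** Between-visit correlation r from 0.3 to 0.9, equal for every pair of visits; for illustration, an effect of 0.5 SD.

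**1. The plan's own figures.** The two-proportion formula for 30% v 5% gives 36 per arm uncorrected and 43 with continuity correction, close to the stated 44. Patient flow: 56 − 6 = 50; 52 − 5 = 47; 50 + 47 = 97; 11/108 = 10.2% lost (10.7% control, 9.6% intervention).

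**2. Power for lymphedema.** At 30% v 5%, power is about 91% with 50 v 47 and about 94% with 56 v 52. Both exceed the planned 80%.

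**3. Gain from keeping the lost patients, without using T0 to adjust the arm contrast.** In units of the outcome variance:

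- completers: 1/50 + 1/47 = 0.04128;
- all enrolled: 1/56 + 1/52 = 0.03709;
- ratio: 0.03709/0.04128 = 0.8985, so the completers' standard error is √(1/0.8985) = 1.055 times that with all 108.

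If earlier visits explain a share R² of the T2 variance, each arm's T2 mean has variance (1 − R²)/m + R²/n, with m completers of n enrolled. Relative to the two-sample test, this is 1 − 0.1015 × R². R² is r² if a patient left before T1 and 2r²/(1 + r) if she left after it.

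| r | variance ratio, lost before T1 | variance ratio, lost after T1 |
|---|---|---|
| 0.3 | 0.991 | 0.986 |
| 0.5 | 0.975 | 0.966 |
| 0.7 | 0.950 | 0.942 |
| 0.9 | 0.918 | 0.913 |

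The gain is about 1% to 9%.

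**4. Gain when T0 is also used (common baseline mean).** With completers alone the ratio is 1 − r². The last column is the generalised least-squares result when all 11 left after T1.

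| r | completers, or all 11 lost before T1 | all 11 lost after T1 |
|---|---|---|
| 0.3 | 0.91 | 0.905 |
| 0.5 | 0.75 | 0.742 |
| 0.7 | 0.51 | 0.501 |
| 0.9 | 0.19 | 0.186 |

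The lost patients change the ratio by at most about 0.01; T0 does the rest. At 0.5 SD, power is 69% for the two-sample test, 73% with the model at r = 0.3 and 81% to 82% at r = 0.5.

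**5. Lymphedema and the 11 unknown outcomes (uncorrected chi-square).** Completer counts come from planning rates: 30% of 50 = 15 or 21.4% of 50 ≈ 11 in controls, and 5% of 47 ≈ 2 in the intervention arm.

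| Scenario | Control | Intervention | p |
|---|---|---|---|
| 30% v 5%, completers | 15/50 | 2/47 | 0.0009 |
| about 30% among the lost in both arms | 17/56 | 4/52 | 0.003 |
| 0 of 6 and 4 of 5 lost affected | 15/56 | 6/52 | 0.045 |
| 0 of 6 and 5 of 5 lost affected | 15/56 | 7/52 | 0.086 |
| 21.4% v 5%, completers | 11/50 | 2/47 | 0.010 |
| 0 of 6 and 2 of 5 lost affected | 11/56 | 4/52 | 0.073 |
| 0 of 6 and 5 of 5 lost affected | 11/56 | 7/52 | 0.39 |

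These are scenarios built on planning rates, not predictions.

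**The case against.** The strongest reply is that section 4 never says the tests are run visit by visit, and section 5 says that 97 patients finished, not that 97 were analysed. A t-test can be run on imputed data, and lymphedema could be counted at any time up to T2. Handling of missing data may sit in an analysis plan that is not shown. This stands as a caution: the 97 is the natural reading of the named tests, not a stated fact. It does not remove the point, because none of those tests uses T0 or links visits.

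It is also fair that loss was half the planned 20%, was similar in the two arms, and left more than 44 per arm. A reader might infer that the trial is underpowered or that symptomatic patients dropped out. The protocol supports neither: power is about 91%, and no reasons for loss are given.

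A reader might also infer that valuable T1 data are being thrown away. The timing of the losses is not stated in the text, and the flow figure is not shown. If all 11 left before T1, there is nothing from T1 to rescue.

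Finally, the p-values of 0.086 and 0.39 are tempting as a measure of what a repeated-measures model would correct. They are not. They describe loss that depends on the unseen outcome, which such a model does not address. Nor would an unweighted logistic GEE help: it does not relax the missing-data assumption. With about 2 planned intervention cases, an arm-by-visit logistic model may fail to converge.

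**Conclusion.** The point holds in a limited form. For the continuous outcomes, section 4 chooses a method that discards baseline information the trial collects. The T2 variance would fall to about 0.91 of the two-sample value at r = 0.3 and about 0.75 at r = 0.5. Both figures rest on assumed, equal between-visit correlations. The benefit is mainly precision from T0; keeping the 11 lost patients is a minor addition, with a weaker missing-data assumption as a further advantage.

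For lymphedema there is no power shortfall and no evidence of bias. What remains is sensitivity. At the planned 30% v 5%, with no lost control affected, significance is lost only if all 5 lost intervention patients are affected. At 21.4% in controls, 2 of the 5 are enough. That justifies showing the table, not replacing the test.

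**What to change.** - **Continuous outcomes** (limb volume difference, grip strength, range of motion, DASH, FACT-B): replace the two-sample tests by one likelihood-based linear mixed model per outcome, on all 108 patients by allocated group. Use T0, T1 and T2 as responses with a common baseline mean, or T0 as a covariate. Report the arm contrast at T2. Do not use classical repeated-measures ANOVA, which drops incomplete patients and returns to 97.
- **Binary lymphedema**: keep the simple comparison at T2. Add a tipping-point table over all combinations of 0 to 6 affected among the lost controls and 0 to 5 among the lost intervention patients. Do not substitute an unweighted GEE.
- **Patient flow**: state how many of the 11 have T1 data.

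The cost is revised wording in section 4 and some analysis work; no new patients, visits or measurements. Reporting becomes slightly more complex. Because section 5 already reports patient flow, the revision should be dated and the tests named in section 4 shown alongside. The model does not by itself deal with the allocation of four medical groups in section 2.4, so its standard errors still need that question answered separately.

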#### 5 RESULTS

In this study, a total of 108 patients completed the baseline survey (T0), 56 in the control group and 52 in the intervention group. A total of 11 patients fell off during the study (6 in the control group and 5 in the intervention group), and a total of 97 patients completed the study (50 in the control group and 47 in the intervention group), as shown in Figure 1.
